## List of Abbreviations

Abbreviation	Definition
AE	adverse event
ALT	alanine aminotransferase
AST	aspartate aminotransferase
AUC 0-∞	area under the concentration-time curve extrapolated to infinity
AUC 0-t	area under the concentration-time curve from time 0 until the last quantifiable concentration
AUC 0-ti	area under the concentration-time curve from time 0 until the last timepoint during the first interdialytic interval
AUC 0-24h	area under the concentration-time curve from time 0 until 24 hours postdose
AUC 0-44h	area under the concentration-time curve from time 0 until 44 hours postdose
BMI	body mass index
CDISC	Clinical Data Interchange Standards Consortium
CFR	Code of Federal Regulations
CKD	Chronic Kidney Disease
CL D	estimated hemodialysis clearance
CL D, Recovery	estimated hemodialysis recovery clearance, where: CL D, Recovery = Amount Recovered in Dialysate/Inlet AUC t0-t1
CL/F	total body clearance
C max	maximum concentration
CRU	Clinical Research Unit
CS	clinically significant
CYP	cytochrome P450
ECG	electrocardiogram
eCRF	electronic Case Report Form
eGFR	estimated glomerular filtration rate
ER D	hemodialysis extraction ratio
ESRD	end-stage renal disease
ET	Early Termination
FDA	Food and Drug Administration
FSH	follicle stimulating hormone

Abbreviation	Definition
GCP	Good Clinical Practice
HBsAg	hepatitis B surface antigen
HCV	hepatitis C virus
HD	hemodialysis
HDPE	high-density polyethylene
HIV	human immunodeficiency virus
IB	Investigator's Brochure
ICF	Informed Consent Form
ICH	International Conference on Harmonisation
IND	Investigational New Drug
Inlet AUC t0-t1	area under the concentration-time curve from start of dialysis (t0) to the end of dialysis (t1) based on inflow concentrations
IRB	Institutional Review Board
MDRD	Modification of Diet in Renal Disease
MedDRA	Medical Dictionary for Regulatory Activities
MR	mineralocorticoid receptor
MRA	mineralocorticoid receptor antagonist
MTD	maximum tolerated dose
MWF	Monday, Wednesday, Friday
n	number of non-missing observations
NCS	not clinically significant
Outlet AUC t0-t1	area under the concentration-time curve from start of dialysis (t0) to the end of dialysis (t1) based on outflow concentrations
Outlet:Inlet Concentration Ratio	ratio of outflow to inflow concentrations based on time-matched inflow and outflow sample

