**Figure 3-1 Study Design Schematic for Part 1**

Abbreviations: CRU = clinical research unit; PK = pharmacokinetic.

##### Part 2

[figure not shown]
In Part 2, a single cohort (Cohort 2) of 6 HD patients will receive a single dose of 0.5 mg KBP-5074 on the same day of HD (immediately after the HD). Following dosing, patients will be followed for 13 days for PK and safety assessments (see Table 12-2). The PK

samples will be obtained relative to dose administration as follows (All PK samples will be collected within  $\pm 5$  minutes of the nominal time unless otherwise specified):

- During the interdialytic interval (using a venous stick or cannula) immediately predose (at time 0 [-5 min]; collected immediately prior to dosing, but following the termination of a previous dialysis session), 2, 4, 6, 8, 10, 12, 18, and 24 hours postdose;
- During the second HD session at 44 (immediately prior to HD [using a venous stick or cannula; -5 min] and 5 minutes after the start of HD [inlet {arterial;  $\pm 1$  min} and outlet {venous;  $\pm 1$  min} samples]), 44.25, 44.5, 46, and 47 hours postdose, and at the end of the second HD session;
- Following dialysis at 48.5, 49, 50, 52, 72, 96, 120, 168, 216, 264, and 312 hours postdose.

[figure not shown]
A study design schematic for a Monday, Wednesday, Friday (MWF) and Tuesday, Thursday, Saturday (TTS) HD schedule for Part 2 is presented in [Figure 3-2](#) and [Figure 3-3](#), respectively.

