To address the long elimination half-life of KBP-5074, the current study will evaluate the PK following a single oral dose of KBP-5074. This dose will be administered following a dialysis session in Part 2. This single-dose approach has been used in the PK assessment for compound with relative long  $t_{1/2}$  in patients requiring HD. Pharmacokinetic assessments will be performed during the subsequent interdialytic interval (approximately 44 hours), during the following dialysis session (approximately 4 hours), and through 312 hours postdose.

This approach will allow for a limited estimation of KBP-5074 PK parameters during the interdialytic period. In addition it will allow for estimation of parameters related to hemodialysis clearance of KBP-5074 (e.g., hemodialysis extraction ratio and hemodialysis clearance, hemodialysis recovery clearance). Finally, this approach will provide a full single-dose PK profile of KBP-5074 collected over multiple dialysis sessions and interdialytic intervals. This full PK profile can be compared to previous single-dose profiles in healthy patients and renally-impaired patients not undergoing hemodialysis.

Safety and tolerability will be assessed through physical examination findings, vital signs, 12-lead ECGs, clinical laboratory findings, and monitoring of AEs. The PK of KBP-5074 in

Part 2 will be assessed during the interdialytic period, during dialysis, and overall by obtaining blood samples, dialysate samples, and by calculating appropriate PK parameters.

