### **Pharmacokinetic Blood Collection and Processing**

Blood samples for the PK analysis of KBP-5074 will be collected at the timepoints specified in [Table 12-1](#) and [Table 12-2](#) for Part 1 and Part 2, respectively. In Part 1, all blood samples will be taken by either direct venipuncture or an indwelling cannula inserted in a forearm vein. In Part 2, blood samples will be taken by either direct venipuncture or an indwelling cannula inserted in a forearm vein during the interdialytic interval and following HD. While HD patients are undergoing dialysis treatment, blood samples must be drawn from the predialyzer (inlet [arterial line]) and postdialyzer (outlet [venous line]) at the timepoints specified in [Table 12-2](#). Blood samples will be collected into labeled tubes containing sodium heparin.

In Part 2, serial PK samples will initially be collected during the postdose interdialytic interval (through approximately 44 hours postdose). Approximately 44 hours following dose administration, the next dialysis session will occur. Serial blood samples (inlet and outlet) as well as dialysate samples will be collected for the duration of this dialysis session (from approximately 44 hours postdose through approximately 48 hours postdose). Additional serial PK samples will be collected following this dialysis session through 312 hours postdose (see [Table 12-2](#)).

Immediately after the sample is collected, the tube should be gently inverted 5 to 8 times to thoroughly mix the anticoagulant and then placed upright in a cryoblock or test tube rack surrounded by ice until centrifugation. Samples will be centrifuged at  $1500 \times g$  for 10 minutes at approximately  $4^{\circ}\text{C}$  within 30 minutes of collection. The resultant plasma will be divided into 2 equal aliquots, placed in individual cryovials, and immediately frozen at  $-70^{\circ}\text{C}$  or colder within 1 hour of collection. The samples will be kept frozen at  $-70^{\circ}\text{C}$  or colder pending shipment to the bioanalytical laboratory. Additional details, including the acceptance of shipments by the bioanalytical laboratory, will be provided in a separate laboratory manual.

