## Part 2:

The following PK parameters will be calculated using noncompartmental methods, whenever possible, based on plasma KBP-5074 concentrations during the initial interdialytic interval:

During Interdialytic Interval	
PK Parameter	Definition
$C_{max}$	maximum concentration
$t_{max}$	time to maximum concentration
$AUC_{0-24h}$	area under the concentration-time curve from time 0 until 24 hours postdose, calculated using the linear trapezoidal rule for increasing values, and the log trapezoidal rule for decreasing values
$AUC_{0-44h}$	area under the concentration-time curve from time 0 until 44 hours postdose, calculated using the linear trapezoidal rule for increasing values, and the log trapezoidal rule for decreasing values
$AUC_{0-ti}$	area under the concentration-time curve from time 0 until the last timepoint during the first interdialytic interval, calculated using the linear trapezoidal rule for increasing values, and the log trapezoidal rule for decreasing values
$\lambda_z$	apparent terminal elimination rate constant
$t_{1/2}$	terminal elimination phase half-life, calculated as $\ln(2)/\lambda_z$

The following PK parameters will be calculated using noncompartmental methods, whenever possible, based on plasma KBP-5074 concentrations during dialysis and overall:

During Dialysis	
PK Parameter	Definition
Inlet $AUC_{t0-t1}$	area under the concentration-time curve from start of dialysis ( $t_0$ ) to the end of dialysis ( $t_1$ ) based on inflow concentrations. AUC will be calculated using the linear trapezoidal rule for increasing values, and the log trapezoidal rule for decreasing values
Outlet $AUC_{t0-t1}$	area under the concentration-time curve from start of dialysis ( $t_0$ ) to the end of dialysis ( $t_1$ ) based on outflow concentrations. AUC will be calculated using the linear trapezoidal rule for increasing values, and the log trapezoidal rule for decreasing values.
Outlet:Inlet Concentration Ratio	ratio of outflow to inflow concentrations based on time-matched inflow and outflow samples
Outlet:Inlet AUC Ratio	ratio of Outlet $AUC_{t0-t1}$ to Inlet $AUC_{t0-t1}$
$CL_{D, Recovery}$	estimated hemodialysis recovery clearance, where: $CL_{D, Recovery} = \text{Amount Recovered in Dialysate} / \text{Inlet } AUC_{t0-t1}$

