Patient should be resting in a semi-recumbent position for at least 5 minutes prior to ECG.

Blood pressure, heart rate, respiratory rate and oral temperature will be measured in patients in a semi-recumbent position for at least 5 minutes.

Clinical laboratory samples include: hematology, clinical chemistry, liver function, and urinalysis.

Dosing will be based on the post dialysis weight from the last dialysis session prior to dosing.

Blood samples for the determination of KBP-5074 concentrations and PK analysis will be collected relative to dose administration as follows (All PK samples will be collected within ±5 minutes of the nominal time unless otherwise specified):

- During the interdialytic interval (using a venous stick or cannula) immediately predose (at time 0 [-5 min]; collected immediately prior to dosing, but following the termination of a previous dialysis session), 2, 4, 6, 8, 10, 12, 18, and 24 hours postdose;
- During the second HD session at 44 (immediately prior to HD [using a venous stick or cannula; -5 min] and 5 minutes after the start of HD [inlet {arterial; ±1 min} and outlet {venous; ±1 min} samples]), 44.25, 44.5, 46, and 47 hours postdose, and at the end of the second HD session;
- Following dialysis (using a venous stick or cannula) at 48.5, 49, 50, 52, 72, 96, 120, 168, 216, 264, and 312 hours postdose.

Cumulative dialysate will be collected and weight/volume determined for the following intervals: 44 to 44.5 hours, 44.5 to 45 hours, 45 to 46 hours, 46 to 47 hours, and 47 to 48 hours postdose. The dialysate collection will end at the end of dialysis (rather than at 48 hours) if a patient has dialysis for <4 hours. An additional sample may be collected until the end of dialysis for sessions lasting longer than 4 hours. The cumulative volume of dialysate collected during each interval will be documented. A 25 mL aliquot will be collected at the end of each interval for determination of KBP-5074 concentration.

Serum and plasma samples for biomarkers (aldosterone and serum potassium) will be collected at the following time points (All biomarker samples will be collected within  $\pm 5$  minutes of the nominal time unless otherwise specified): predose (at time 0 [-5 min], collected immediately prior to dosing) and 2, 6, 12, 24, 48, 72, 96, 120, 168, 216, 264, and 312 hours post dose.

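### Dialysate collection after 4 hours is optional, but the recovery clearance divides by an inlet AUC that runs to the end of dialysis, so it is biased low in longer sessions

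*Protocol*

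**What the plan says.** **Formula.** Section 7.1 (Part 2, During Dialysis) lists CL_D,Recovery, the "estimated hemodialysis recovery clearance", as the amount of drug found in the dialysate over Inlet AUC t0–t1. Both there and in the List of Abbreviations, that AUC is the "area under the concentration-time curve from start of dialysis (t0) to the end of dialysis (t1) based on inflow concentrations". Its upper limit is the end of the session, not a fixed clock time.

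**Blood.** Section 3.1 and Table 12-2 footnote 7 schedule samples during the second session up to 47 hours postdose "and at the end of the second HD session". Whatever the session length, there is a sample to close the AUC at t1.

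**Dialysate.** Table 12-2 footnote 8 sets five collection intervals starting at 44 hours, the last two being "46 to 47 hours, and 47 to 48 hours postdose". For sessions under 4 hours it matches the collection to the session: "The dialysate collection will end at the end of dialysis (rather than at 48 hours"). For sessions over 4 hours it says only: "An additional sample may be collected until the end of dialysis for sessions lasting longer than 4 hours".

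**Body text.** Section 6.1.5.1 says that serial blood samples "as well as dialysate samples will be collected for the duration of this dialysis session", and describes the session as running from roughly 44 to roughly 48 hours postdose. Section 3.1.1 likewise places the assessments "during the following dialysis session (approximately 4 hours").

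**The concern.** A recovery clearance is interpretable only if the amount in the numerator and the AUC in the denominator cover the same time. Footnote 8 secures this for short sessions but leaves it to choice for long ones, and nothing in the protocol shortens the inlet AUC when the extra dialysate is not taken. The footnote also permits something that section 6.1.5.1, read for a session running past 48 hours, does not.

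Pharmacokinetics during the dialysis session is part of a primary objective of Part 2 (section 2.1), and section 3.1.1 names recovery clearance among the quantities the design should deliver. It is the only listed clearance based on drug actually found in dialysate. Part 2 has six patients, so one affected patient is a sixth of the summary. With up to four centers, an optional collection can also be handled differently from site to site. CL_D and ER_D come from blood concentrations (and, for CL_D, blood flow) and are untouched. A truncated recovery value could therefore make the two clearance estimates appear to disagree for a purely procedural reason.

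**Working it through.** The protocol gives no figure on this point, so there is none to reproduce. The size of the bias follows from the definitions.

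**Inputs from the protocol**
- Mandatory dialysate: 44 to 48 h, that is, the first 4 h of the session (Table 12-2 footnote 8).
- Denominator: inlet AUC from start to end of dialysis (section 7.1; List of Abbreviations).
- Part 2 cohort: 6 patients (section 3.1).
- Half-life: average above 50 h (sections 1.3 and 3.1.1).

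**Assumptions**
- Dialysis clearance CL is constant within the session.
- Session length T is 4.25, 4.5 or 5 h. The protocol gives no distribution or maximum.
- Inlet concentration is either constant or falls exponentially with a half-life of 50, 10 or 2 h. The protocol gives no on-dialysis half-life, so this is a range.

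**Formula**

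Amount collected without the tail = CL × AUC(0–4). Reported value = CL × AUC(0–4) / AUC(0–T). Hence

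relative bias = AUC(0–4)/AUC(0–T) − 1.

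- Constant inlet concentration: bias = 4/T − 1.
- Declining inlet concentration, with k = ln 2 / half-life: bias = (1 − e^(−4k)) / (1 − e^(−kT)) − 1.

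**Worked case, T = 4.5 h**
- Constant inlet: 4/4.5 − 1 = −11.1%.
- Half-life 50 h: k = 0.01386 per h; (1 − e^(−0.05545)) / (1 − e^(−0.06238)) − 1 = 0.05394/0.06048 − 1 = −10.8%.

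**Bias in one affected patient**

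| Inlet concentration during dialysis | T = 4.25 h | T = 4.5 h | T = 5 h |
|---|---|---|---|
| Constant | −5.9% | −11.1% | −20.0% |
| Half-life 50 h | −5.7% | −10.8% | −19.4% |
| Half-life 10 h | −5.1% | −9.6% | −17.3% |
| Half-life 2 h | −2.7% | −5.0% | −8.9% |

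For T of 4 h or less, or with the tail collected, the bias is zero. The sign is negative in every affected case.

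**Effect on the mean of six**, with equal true clearance and m affected sessions of 4.5 h at constant inlet concentration: m/6 × 11.1%, which gives 1.9% low for m = 1, 5.6% for m = 3 and 11.1% for m = 6.

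**After correction.** If the tail is collected, both windows run to T. If instead the AUC is cut at the end of the last dialysate interval, both stop there. Under the constant-clearance model the ratio equals CL either way, so the bias is 0%.

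**The case against.** The case for leaving this alone has four parts.

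- **The SAP can deal with it.** Section 7.1 refers to the SAP for further calculation detail, and matching the windows when a sample is missing could be such a detail. Cutting the AUC does remove the bias under constant clearance, and the blood samples at 47 h and at session end allow interpolation to the end of the last dialysate interval. No listed parameter is a total amount or fraction recovered. This stands in part: the loss is not fatal to CL_D,Recovery. But the protocol's own formula fixes t1 at the end of dialysis and nothing in it permits a shorter window. The problem is a stated sampling rule that does not fit a stated formula, not a missing detail. Dialysate discarded after 48 h cannot be recovered by any analysis rule.
- **The conflict with section 6.1.5.1 is mild.** That section glosses the session as about 44 to 48 h, which is what footnote 8 requires. This stands for sessions that end by 48 h. It does not help for longer ones, which footnote 8 itself foresees.
- **The effect may never occur.** The planned session is about 4 h, and the number running longer is unknown. This stands fully and limits the weight of the point.
- **Other measures of dialytic removal are unaffected, and the analysis is descriptive.** CL_D, ER_D and the outlet:inlet ratios do not use dialysate, and no test or threshold depends on CL_D,Recovery. This is true, and it confines the damage to one parameter. That parameter still serves a primary objective and would be reported wrongly.

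**Conclusion.** The concern holds. As written, the protocol allows a 4-hour dialysate amount to be divided by an inlet AUC over a longer session, which always understates CL_D,Recovery. In an affected patient the shortfall is 5.9%, 11.1% and 20.0% for sessions of 4.25, 4.5 and 5 h at constant inlet concentration. It is almost the same at the 50 h half-life, and about half or less of that if the inlet concentration fell with a half-life as short as 2 h. These figures assume constant dialysis clearance and no tail collection.

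The effect on the cohort depends on how many of the six sessions exceed 4 h without the tail, which the protocol does not tell us; it may be nil. Only CL_D,Recovery is touched. The point merits correction because the error is one-directional, concerns a parameter under a primary objective in a very small cohort, and costs almost nothing to prevent.

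**What to change.** 1. In Table 12-2 footnote 8, replace *may* with *will* in the sentence on sessions longer than 4 hours, so that dialysate is collected to the actual end of dialysis in every patient, in agreement with section 6.1.5.1.
2. In section 7.1, add one sentence under CL_D,Recovery: if dialysate was not collected to the end of dialysis, the inlet AUC used for this parameter ends at the actual end of the last dialysate interval, with the inlet concentration at that time interpolated from the neighboring samples.

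The first change keeps the data; the second keeps the ratio valid if the first fails in practice.

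The cost is one word, one sentence, and one further dialysate interval with a 25 mL aliquot in sessions over 4 hours. No new visit is needed, and clinical management does not change.

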## 2 Study Objectives

### 2.1 Primary Objectives

The primary objectives of this study are:

- To evaluate the safety and tolerability of a single dose of KBP-5074 in HD and non-HD patients with severe CKD.
- To evaluate the PK of KBP-5074 following a single oral dose administration of 0.5 mg KBP-5074 in non-HD patients with severe CKD (defined as eGFR  $\geq 15$  mL/min/1.73 m^2 and  $\leq 29$  mL/min/1.73 m^2 based on the MDRD equation) in Part 1 of the study.
- To evaluate the PK of KBP-5074 following a single oral dose of 0.5 mg KBP-5074 administered to HD patients in Part 2 of the study. Pharmacokinetics will be evaluated during the following periods in Part 2:
  - During a single interdialytic interval (from approximately 0 to 44 hours postdose).
  - During a single dialysis session (from approximately 44 to 48 hours postdose).
  - Overall through washout (from the time of dose administration through 312 hours postdose, as data permit).

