### 6.1.5 Clinical Laboratory Tests

Laboratory measurements (including hematology, clinical chemistry, and urinalysis) will be performed at the timepoints specified in [Table 12-1](#) and [Table 12-2](#) for Part 1 and Part 2, respectively. Clinical laboratory parameters for analysis are presented in [Table 6-1](#).

Serum potassium levels of study patients will be closely monitored throughout this study. To ensure quick access to laboratory results, serum potassium levels will be tested in local laboratories in this study. If serum potassium is  $>5.6$  mmol/L during a scheduled/unscheduled visit, serum potassium levels should be repeated as early as feasible (no more than 48 hours). For patients who currently take potassium supplementation, it is recommended that the repeat test of serum potassium be taken 24 hours after the stopping of potassium supplementation if the Investigator considers it clinically safe and feasible.

A single repeat of laboratory testing at Screening and Day -1 are allowed to rule out lab error (i.e. hemolysis in potassium specimens).

Urine or serum pregnancy tests (all female patients) and FSH tests (postmenopausal female patients) will be performed at the timepoints specified in [Table 12-1](#) and [Table 12-2](#) for Part 1 and Part 2, respectively.

An alcohol breath test and drug screen will be administered to all patients at the timepoints specified in [Table 12-1](#) and [Table 12-2](#) for Part 1 and Part 2, respectively.

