**Table 12-2 Schedule of Events for Part 2**

Day	Screening	Patients Resident at CRU																				Outpatient Visits						EOS 				
	-28 to -2	-1	1						2						3						4	5	6	8	10	12	14					
Hours		-24	0	2	4	6	8	10	12	18	24	44	44.25	44.5	45	46	47	48	48.5	49	50	52	72	96	120	168	216	264	312			
Admission to CRU		X																														
Discharge from CRU																							X 									
Informed Consent	X																															
Eligibility Assessment	X	X																														
Medical History	X																															
Demographics	X																															
Height (cm), Weight (kg), BMI	X																															
Previous Medications	X	X																														
Concomitant Medications			X																													
Physical Examination	X	X 																												X		
Single 12-lead ECG 	X		X			X																								X		
Vital Signs (BP, PR, RR, T) 	X	X	X	X	X	X	X		X		X							X							X	X	X	X	X	X	X	X
AE Assessment	X	X	X																													
Clinical Laboratory Samples 	X	X				X																								X		
Dose Administration 			X																													

Day	Screening	Patients Resident at CRU																				Outpatient Visits						EOS 		
	-28 to -2	-1	1						2						3						4	5	6	8	10	12	14			
Hours		-24	0	2	4	6	8	10	12	18	24	44	44.25	44.5	45	46	47	48	48.5	49	50	52	72	96	120	168	216	264	312	
PK Blood Samples 			X	X	X	X	X	X	X	X	X	X	X	X		X	X	X	X	X	X	X	X	X	X	X	X	X	X	X
Dialysate Sampling 													X	X	X	X	X													
Biomarker Samples (Aldosterone and Potassium) 			X	X		X			X		X												X	X	X	X	X	X	X	X
HIV, Hepatitis B and C Screen	X																													
Drug/Alcohol Screen 	X	X 																												
Serum/Urine Pregnancy Test 	X	X																												X

AE= adverse event; BP = blood pressure; CRU = clinical research unit; ECG = electrocardiogram; HIV = human immunodeficiency virus; PR = pulse rate; PK = pharmacokinetics; RR = respiratory rate; T = temperature.

Note: baseline is the Day 1 predose (time 0) sample.

Patients in Part 2 will be discharged from the CRU after the dialysate collection on Day 3.

Brief physical examination will be conducted at Check-in (Day -1).

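### In Part 2 no scheduled potassium sample covers the last 20 h of the 44 h interdialytic interval, although blood is already drawn immediately before dialysis at 44 h

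*Protocol*

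**What the plan says.** Protocol Table 12-2, footnote 9, lists the Part 2 biomarker samples (plasma aldosterone and serum potassium) as predose "and 2, 6, 12, 24, 48, 72, 96, 120, 168, 216, 264, and 312 hours post dose". The window is tight: "All biomarker samples will be collected within" 5 minutes either side of nominal. Table 12-1, footnote 7, gives the same list for the non-dialysis patients of Part 1.

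Section 2.1 defines the Part 2 periods: "During a single interdialytic interval (from approximately 0 to 44 hours postdose") and "During a single dialysis session (from approximately 44 to 48 hours postdose"). Section 6.1.5.1 places the inlet, outlet and dialysate sampling in the same session, "from approximately 44 hours postdose through approximately 48 hours postdose".

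The PK schedule does follow the dialysis timetable. Table 12-2, footnote 7, includes a draw "During the second HD session at 44 (immediately prior to HD [using a venous stick or cannula; -5 min"].

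On potassium safety, Section 6.1.5 promises: "Serum potassium levels of study patients will be closely monitored throughout this study". It asks for a repeat test when a value exceeds 5.6 mmol/L at a scheduled or unscheduled visit. Change in potassium and aldosterone from baseline is the secondary objective (Section 2.2). Table 12-2 states: "Note: baseline is the Day 1 predose (time 0) sample". Because the dose follows a dialysis session directly (Section 5.2), that baseline is a post-dialysis value.

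**The concern.** The biomarker times suit a patient who is not dialysed. Between dialysis sessions potassium accumulates, so the level just before the next session is the one of most interest for safety. The Part 2 schedule samples well before that moment and then after most or all of the session has passed.

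Potassium elevation is the risk that Section 1.1 names for existing drugs of this class. Safety is a primary objective and potassium change is the secondary one. The potassium ceiling at Screening and Check-in (inclusion criterion 4) applies to Part 1 only, so the dialysis patients also lack that check at entry. A Part 2 report could describe potassium after dosing without any scheduled value from the late part of the only interval that the protocol studies intensively. It would also have an end-of-interval drug concentration with no potassium value to set beside it.

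**Working it through.** The protocol states no sample size, power or error rate for this endpoint, so there is no figure to reproduce. The check is a comparison of times.

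**Inputs**
- Biomarker times (Table 12-2, footnote 9): 0, 2, 6, 12, 24, 48, 72, 96, 120, 168, 216, 264, 312 h, each ±5 min. I take the times from the footnote because column alignment in the table is not reliable in the text copy. The row has eight crosses after 24 h, as the footnote requires, and none at 44 h.
- Interdialytic interval: about 0 to 44 h. Dialysis session: about 44 to 48 h (Section 2.1).
- Clinical laboratory row in Part 2: Screening, Day -1, 6 h and end of study (Day 14). Potassium is part of that chemistry panel (Table 6-1).
- PK draw: 44 h, immediately before dialysis, by venous stick or cannula.

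**First interval**
- The only pair of consecutive biomarker times that encloses 44 h is 24 and 48 h.
- Time from the last potassium value to the start of dialysis: 44 − 24 = 20 h.
- Share of the interval with no scheduled value: 20 / 44 = 45%.
- The ±5 min window does not let the 24 h or 48 h sample move to 44 h.
- The chemistry panel gives nothing between 6 h and Day 14.

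None of this needs an assumption beyond the protocol's own 44 to 48 h session. The 48 h sample is only nominally at the end of dialysis, because footnote 8 allows sessions shorter or longer than 4 h. It may fall during or after the session, but not before it.

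**Can a later sample stand in?**
The 312 h sample may lie late in an interval. Assume dialysis on Days 1, 3, 5, 8, 10 and 12, with sessions ending at the clock time of dosing. The last session before 312 h then ends at (12 − 1) × 24 = 264 h, so 312 h is 48 h after dialysis. Little drug may remain by then. Section 1.3 gives an average half-life above 50 h in healthy subjects; I take 50 to 100 h, the upper end being an assumption. With simple decay, remaining fraction = 0.5^(t / half-life):

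| Time | Half-life 50 h | Half-life 100 h |
|---|---|---|
| 44 h | 54% | 74% |
| 312 h | 1% | 12% |

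The 312 h sample therefore does not replace one at 44 h.

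**After the fix**
The 24 h gap (24 to 48 h) splits into 44 − 24 = 20 h and 48 − 44 = 4 h, with one value at the end of the interval.

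**The case against.** The strongest objection is about interpretation. Baseline is post-dialysis, the endpoint is post-baseline minus baseline (Section 7.7.3), and Part 2 is one open-label cohort of 6 without a control interval. If potassium accumulates between sessions, the 44 h change from baseline rises with or without drug. The 48 h sample, by contrast, is nominally like-for-like with baseline. This stands. It limits what a 44 h change can show, but not the value of the absolute level for safety review. It is also a reason to leave the later samples where they are. Moving them would lose that comparison and separate them from PK draws that are themselves fixed at ±5 min.

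The protocol also does not say that potassium peaks before dialysis. That is correct: the sampling gap is a fact, and the peak is an inference.

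A reader might infer more than the documents support:

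- *No session in the study has a pre-dialysis potassium value.* The protocol times only the Day 1 session and the one at 44 to 48 h. When outpatient sessions run relative to the later visits is not stated, so this depends on assumed chair times.
- *All later samples sit at a post-dialysis low.* Even on the calendar assumed above, 72 and 120 h are 24 h after a session and 312 h is 48 h after one.
- *The 5.6 mmol/L repeat rule cannot be triggered before dialysis.* It covers unscheduled visits, and Section 6.1 allows additional safety assessments. What is missing is a scheduled test.
- *Aldosterone has the same problem.* The accumulation argument concerns potassium. The only case for aldosterone at 44 h is pairing it with the PK value.

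**Conclusion.** The point holds for the first interdialytic interval and for potassium. The last 20 of 44 h (45%) has no scheduled potassium value, while blood is already being drawn at the end of that stretch for PK. The timing gap rests only on the protocol's stated times. The claim that this is where potassium is highest rests on the expectation of accumulation between sessions. PK interpretation is unaffected. What is weakened is the scheduled safety observation of potassium and the descriptive secondary endpoint in Part 2. It is worth correcting mainly because the correction is cheap.

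**What to change.** In Table 12-2 and footnote 9, add serum potassium to the existing 44 h pre-dialysis venous draw, with aldosterone optional for pairing with the PK value. Report it as a separate, labelled pre-dialysis time point, mainly as an absolute value. If change from baseline is also shown, note that it mixes any drug effect with ordinary interdialytic accumulation. Leave the 48 h and later biomarker times unchanged.

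Cost: one extra tube for serum, because the PK tube contains sodium heparin, or two if plasma aldosterone is taken as well. No new venipuncture or visit is needed, since patients are still confined at 44 h (Section 3.1: until 52 h). The remaining limitation is that the value cannot by itself be attributed to drug.
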